13.5 CHANGES IN THE PROTOCOL

Once the protocol has been approved by the UCSF IRB, any changes to the protocol must be documented in the form of an amendment. The amendment must be signed by the Investigator and approved by PRC and the IRB prior to implementation.

If it becomes necessary to alter the protocol to eliminate an immediate hazard to patients, an amendment may be implemented prior to IRB approval. In this circumstance, however, the Investigator must then notify the IRB in writing within five (5) working days after implementation.

The Study Chair and the UCSF study team will be responsible for updating any participating sites.

13.6 HANDLING AND DOCUMENTATION OF CLINICAL SUPPLIES

The UCSF Principal Investigator (Sponsor-Investigator) and each participating site will maintain complete records showing the receipt, dispensation, return, or other disposition of all investigational drugs. The date, quantity and batch or code number of the drug, and the identification of patients to whom study drug has been dispensed by patient number and initials will be included. The sponsor-investigator will maintain written records of any disposition of the study drug.

The Principal Investigator shall not make the investigational drug available to any individuals other than to qualified study patients. Furthermore, the Principal Investigator will not allow the investigational drug to be used in any manner other than that specified in this protocol.

13.7 CASE REPORT FORMS (CRFs)

The Principal Investigator and/or his/her designee will prepare and maintain adequate and accurate participant case histories with observations and data pertinent to the study. Study specific Case Report Forms (CRFs) will document safety and treatment outcomes for safety monitoring and data analysis. All study data will be entered into OnCore® via standardized CRFs in accordance with the CTMS study calendar, using single data entry with a secure access account. The Clinical Research Coordinator (CRC) will complete the CRFs as soon as possible upon completion of the study visit; the Investigator will review and approve the completed CRFs.

The information collected on CRFs shall be identical to that appearing in original source documents. Source documents will be found in the patient's medical records maintained by UCSF personnel. All source documentation should be kept in separate research folders for each patient.

In accordance with federal regulations, the Investigator is responsible for the accuracy and authenticity of all clinical and laboratory data entered onto CRFs. The PI will approve all completed CRFs to attest that the information contained on the CRFs is true and accurate.

All source documentation and CTMS data will be available for review/monitoring by the UCSF DSMC and regulatory agencies.

The Principal Investigator will be responsible for ensuring the accurate capture of study data. At study completion, when the CRFs have been declared to be complete and accurate, the database will be locked. Any changes to the data entered into the CRFs after

that time can only be made by joint written agreement among the Study Chair, the Trial Statistician, and the Protocol Project Manager.

Each participating site will complete study specific CRFs for safety monitoring and data analysis. Each site will enter the study data into OnCore® via standardized CRFs in accordance with the CTMS study calendar, using single data entry with a secure access account. The participating site's Clinical Research Coordinator (CRC) will complete the CRFs; the Investigator will review and approve the completed CRFs – this process must be completed within 3 business days of the visit. Study data from the participating site will be reported and reviewed in aggregate with data from patients enrolled at the coordinating center, UCSF. All source documentation and CTMS data will be available for review/monitoring as needed.

13.8 OVERSIGHT AND MONITORING PLAN

The UCSF Helen Diller Family Comprehensive Cancer Center DSMC will be the monitoring entity for this study. The UCSF DSMC will monitor the study in accordance with the NCI-approved Data and Safety Monitoring Plan (DSMP). The DSMC will routinely review all adverse events and suspected adverse reactions considered "serious". The DSMC will audit study-related activities to ensure that the study is conducted in accordance with the protocol, local standard operating procedures, FDA regulations, and Good Clinical Practice (GCP). Significant results of the DSMC audit will be communicated to the IRB and the appropriate regulatory authorities at the time of continuing review, or in an expedited fashion, as applicable. See Appendix 6 Data and Safety Monitoring Plan for a Phase 2 or 3 Multicenter Institutional Study, for additional information.

13.9 MULTICENTER COMMUNICATION

The UCSF Coordinating Center provides administration, data management, and organizational support for the participating sites in the conduct of a multicenter clinical trial. The UCSF Coordinating Center will also coordinate, at minimum, quarterly conference calls with the participating sites or more frequently as needed to discuss risk assessment. The following issues will be discussed as appropriate:

- Enrollment information
- Adverse events (i.e., new adverse events and updates on unresolved adverse events and new safety information)
- Protocol violations
- Other issues affecting the conduct of the study

13.10 RECORD KEEPING AND RECORD RETENTION

The Principal Investigator is required to maintain adequate records of the disposition of the drug, including dates, quantity, and use by subjects, as well as written records of the disposition of the drug when the study ends.

The Principal Investigator is required to prepare and maintain adequate and accurate case histories that record all observations and other data pertinent to the investigation on each individual administered the investigational drug or employed as a control in the investigation. Case histories include the case report forms and supporting data (e.g., signed and dated consent forms and medical records, such as progress notes of the physician, the individual's hospital chart(s), and the nurses' notes. The case history for each individual shall document that informed consent was obtained prior to participation in the study.

Study documentation includes all CRFs, data correction forms or queries, source documents, Sponsor-Investigator correspondence, monitoring logs/letters, and regulatory documents (e.g., protocol and amendments, IRB correspondence and approval, signed patient consent forms).

Source documents include all recordings of observations or notations of clinical activities and all reports and records necessary for the evaluation and reconstruction of the clinical research study.

In accordance with FDA regulations, the investigator shall retain records for a period of 2 years following the date a marketing application is approved for the drug for the indication for which it is being investigated; or, if no application is to be filed or if the application is not approved for such indication, until 2 years after the investigation is discontinued and FDA is notified.

13.11 REGULATORY DOCUMENTATION

Prior to implementing this protocol at UCSF HDFCCC, the protocol, informed consent form, HIPAA authorization and any other information pertaining to participants must be approved by the UCSF IRB. Prior to implementing this protocol at the participating sites, approval for the UCSF IRB approved protocol must be obtained from the participating site's IRB.

The following documents must be provided to UCSF HDFCCC before the participating site can be initiated and begin enrolling participants:

- Participating Site IRB approval(s) for the protocol, appendices, informed consent form, and HIPAA authorization
- Participating Site IRB approved consent form
- Participating Site IRB membership list
- Participating Site IRB's Federal Wide Assurance number and OHRP Registration number
- Curriculum vitae and medical license for each investigator and consenting professional
- Documentation of Human Subject Research Certification training for investigators and key staff members at the Participating Site
- Participating site laboratory certifications and normals.

Upon receipt of the required documents, UCSF HDFCCC will formally contact the site and grant permission to proceed with enrollment.

14 PROTECTION OF HUMAN SUBJECTS

14.1 PROTECTION FROM UNNECESSARY HARM

Each clinical site is responsible for protecting all subjects involved in human experimentation. This is accomplished through the IRB mechanism and the process of informed consent. The IRB reviews all proposed studies involving human experimentation and ensures that the subject's rights and welfare are protected and that the potential benefits and/or the importance of the knowledge to be gained outweigh the risks to the individual. The IRB also reviews the informed consent document associated with each study in order to ensure that the consent document accurately and clearly communicates the nature of the research to be done and its associated risks and benefits.

14.2 PROTECTION OF PRIVACY

Patients will be informed of the extent to which their confidential health information generated from this study may be used for research purposes. Following this discussion, they will be asked to sign the HIPAA form and informed consent documents. The original signed document will become part of the patient's medical records, and each patient will receive a copy of the signed document. The use and disclosure of protected health information will be limited to the individuals described in the informed consent document.

In order to maintain patient confidentiality, only a site number and patient number will identify all study patients on blood samples and tumor specimens.

Long-term Storage of Samples for Future Research

Samples collected for biomarker assessments are planned to be stored until testing and for up to 5 years after the end of the study at the [name] laboratory at UCSF. All samples will be labeled with unique study ID number, and no personal identifying information will be attached to the sample.

APPENDIX 1: SCHEDULE OF ACTIVITIES

Activities and Forms to be Completed	Screening	Treatment Phase			Post treatment		
	≤42 Days Prior to Randomization	Cycle 1 Day 1	D1 C2-C4, D1 of every 2 cycles starting at C5 to C13 (+/- 7 days)	Every 16 weeks (Starting on C1D1)	End-of-Treatment	Safety Follow-up	At PSA PD by PCWG (+ 28 days)
Screening							
Informed Consent	X						
Medical/Oncological History [3]	X						
Inclusion/Exclusion Criteria	X						
Randomization [4]	X						
Study Treatment Administration							
Apalutamide Administration [5]		240 mg per day taken orally					
SBRT [6]			X				
Assess Study Drug Compliance			X		X		
Laboratory Studies							
Hematology [7]	X	X	X		X		
Blood Chemistry [7]	X	X	X		X		
Serum Albumin	X						
PSA [8]	X	X	X		X	X	
Testosterone	X						
Thyroid-Stimulating Hormone [9]	X	X		X	X		
Efficacy							
ECOG Performance Status	X	X	X		X		X
PSMA PET Scan [10]	X						X

Activities and Forms to be Completed	Screening	Treatment Phase			Posttreatment		
	≤42 Days Prior to Randomization	Cycle 1 Day 1	D1 C2-C4, D1 of every 2 cycles starting at C5 to C13, (+/- 7 days)	Every 16 weeks (Starting on C1D1)	End-of-Treatment [1]	Safety Follow-up [2]	At PSA PD by PCWG (+ 28 days)
Safety							
Physical Examination [12]	X	X	X		X		
Vital Signs (BP and heart rate)	X	X	X		X		
DXA Bone density test (femoral neck and lumbar spine)	X						
Adverse Events		Continuous until 30 days after the last dose of study drug					
Concomitant Medications		Continuous until 30 days after the last dose of study drugs					
Exploratory Biomarkers							
Archival FFPE blocks/slides [11]	X						

C1D1=Cycle 1 Day 1; BICR=blinded independent central review; CT=computed tomography; ECG=electrocardiogram; ECOG=Eastern Cooperative Oncology Group; EQ-5D=Euro QoL; FACT-P=functional assessment of cancer therapy-prostate; FFPE=formalin-fixed paraffin-embedded; PSA=prostate specific antigen

Footnotes

- End-of-Treatment:** These assessments do not need to be completed if they have been performed within 1 week of the last dose of study drug
- Safety Follow-Up:** Patients should be evaluated for safety up to 30 days after the last dose of study drug. All AEs should be followed to their resolution, until the Investigator assesses them as stable, irreversible, or until the patient is lost to follow-up, whichever comes first. If a patient begins a new systemic anti-cancer therapy, the AE reporting period for non-SAEs ends at the time the new treatment is started.
- Medical/Oncological History:** Includes oncologic history, demographics, history of other disease processes (active or resolved) and concomitant illnesses.
- Study Randomization:** The Cycle 1 Day 1 visit can occur on the same day or within 7 days after randomization.
- Apalutamide:** Patients in both treatment arms will receive oral daily apalutamide continuously, starting on Cycle 1 Day 1. One cycle consists of 28 days.
- Stereotactic body radiation therapy (SBRT):** Patients randomized to SBRT arm must begin treatment within 90 days following initiation of apalutamide therapy.
- Samples for Hematology, Blood Chemistry:** All laboratory assessments will be performed by local laboratory. On Cycle 1 Day 1 only, clinical laboratory tests do not need to be repeated if the Screening tests were done within 4 days of Cycle 1 Day 1. See Appendix 2 for complete list of hematology and blood chemistry tests.
- Samples for PSA:** PSA evaluations will be performed by local laboratories. On Cycle 1 Day 1 only, the PSA evaluation does not need to be repeated if the Screening tests were done within 4 days of Cycle 1 Day 1. During the treatment period, PSA will be measured on Day 1 of every cycle (+/- 7 days). During the post-treatment period PSA will be measured every 28 days (+/- 7 days).
- TSH:** TSH will be completed during Screening and Day 1 of each cycle for the first four cycles, then every 4 cycles starting at Cycle 5
- PSMA PET imaging:** Whole body (vertex to toes) PSMA PET imaging will be performed during Screening (within 12 weeks of randomization). At the time of PSA progression by PCWG criteria there is optional follow up PSMA PET scan. PSMA PET imaging may use Ga-PSMA-11 or other PSMA PET tracer. Either PET/MR or PET/CT may be performed.
- Collection of archival primary prostate cancer tissue (optional):** Archival tumor specimens will be collected whenever available.

12. Physical exams may be performed via a telemedicine visit. Vital signs (BP and heart rate) will be self-reported by the patient if the physical exam visit is through telemedicine.

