Primary Objective	To demonstrate whether the proportion of patients with an

	undetectable serum PSA at 6 months following cessation of apalutamide is higher with addition of SBRT to PSMA-avid oligometastatic sites of disease compared to the group of patients receiving apalutamide monotherapy.
Secondary Objectives	
 1. To compare the time to PSA progression by PCWG criteria between treatment arms 2. To evaluate the safety and tolerability of apalutamide in combination with SBRT.
Exploratory Objectives	
 1. To evaluate the genomic factors associated with the presence of oligometastatic disease 2. To evaluate the association between somatic and germline genomic alterations with outcomes on protocol therapy 
Note: The italicized objectives above were discontinued in Protocol v. 8.0. See Section 7.3 for additional information.
 
 3. To characterize the metastatic pattern at baseline and at progression in these patients and to determine whether features of the baseline PSMA-PET scan are associated with treatment outcomes.
Study Design	
This is a randomized (1:1), open-label, phase II clinical trial evaluating the efficacy and safety of apalutamide with or without SBRT to all visible lesions in men with CRPC and oligometastatic disease based upon PSMA-PET imaging. Patients will complete up to 52 weeks of treatment with apalutamide in the absence of disease progression, and will subsequently be followed until PSA progression as defined by PCWG criteria. Following development of PSA progression, patients may undergo repeat PSMA-PET imaging. Treatment at the time of progression will be at the discretion of the treating physician, and can include SBRT for those patients deemed appropriate candidates (whether or not they received prior SBRT) and/or any FDA approved systemic therapy.
 <pre> graph TD A[PSMA PET] --> B[Biopsy of PSMA-avid Lesion] B --> C[Randomize] C -- 1:1 --> D[Arm A] C -- 1:1 --> E[Arm B] D --> F[Apalutamide] E --> G[Apalutamide + SBRT] F --> H[12 months] G --> H H --> I[PSA Progression by PCWG] I --> J[Optional Follow Up PSMA PET] I --> K[Treatment Per Investigator Discretion Off Study] </pre> 
Cut-Point for Analysis of Primary Endpoint: Proportion of Pts With PSA < 0.2 ng/mL at 6 Months Post-Apalutamide Treatment

Number of Patients	60 (apalutamide: 30; apalutamide + SBRT: 30)

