4.4 DURATION OF FOLLOW UP

For safety follow up, patients will be followed for adverse events until 30 days after completion of treatment, removal from study, or until death, whichever occurs first. Patients removed from study for unacceptable treatment related adverse event(s) will be followed until resolution or stabilization of all treatment related adverse events to Grade 2 or lower.

Patients will be followed on study until confirmed PSA progression by PCWG criteria.

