7.1.7 Concomitant Medications/Therapies

All concomitant medication and concurrent therapies will be documented from screening until 30 days after the last dose of study drug. Name, indication for administration, and dates of medication or therapy will be captured.

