8.6 POST-TREATMENT PERIOD UNTIL CONFIRMED PSA PROGRESSION BY PCWG CRITERIA

- Collect blood for PSA measurement every 28 days (+/- 7 days) until confirmed PSA progression by PCWG3 criteria. In the event of disease progression per PCWG3 or initiation of a new non-protocol therapy, patients will be discontinued from the study, and further PSA tracking will no longer be required

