12 STATISTICAL METHODS AND CONSIDERATIONS

12.1 ANALYSIS POPULATIONS

Safety Analysis Population [SAFETY]: All patients who receive at least one dose of study drug, with treatment assignments designated according to actual study treatment received will be the primary population for evaluating safety and treatment compliance and administration.

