12.2.2 Analyses of Secondary Endpoints

Comparison of time to PSA progression will be performed using a two-sided log-rank test. Kaplan-Meier methods will be used to estimate medians for each treatment arm. Cox proportional-hazard models, including the same factors as above, will be used to estimate the hazard ratio and its 95% confidence interval (CI).

Adverse events (AEs) will be graded according to the NCI Common Terminology Criteria for Adverse Events (CTCAE) Version 4.03. All AEs reported from the first dose of study drug until 30 days after the last dose of study drug will be considered as treatment-emergent AEs and will be summarized by treatment arm. For each treatment arm, adverse event incidence rates will be summarized with frequency and percentage, with all patients treated in that treatment arm as the denominator, unless otherwise specified. In addition, AE incidence rates will also be summarized by severity and relationship to study drug. Treatment-related AEs are those judged by the Investigator to be at least possibly related to the study treatment. Adverse events with missing severity or relationship to study drug will be classified as severe and treatment-related, respectively.

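### Section 12.2.2 sets no cut-off at non-protocol therapy, so toxicity from off-study SBRT can be tabulated under the study arm, including apalutamide alone; the expected effect is small

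*Combined protocol and SAP*

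**What the plan says.** Four provisions combine.

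- **Collection.** Section 9.3.2 and Appendix 1 footnote 2 run AE reporting to 30 days after the last dose, with one early stop, for non-serious events: "If a patient begins a new systemic anti-cancer therapy, the AE reporting period for non-SAEs ends at the time the new treatment is started". Local treatment is not named.
- **Therapy at progression.** The Abstract (Study Design) says that treatment at progression "can include SBRT for those patients deemed appropriate candidates (whether or not they received prior SBRT"). Section 3.1 also describes SBRT as something that may be given later, after the study.
- **Analysis window.** Section 12.2.2: "AEs reported from the first dose of study drug until 30 days after the last dose of study drug will be considered as treatment-emergent". These are summarised by arm, with no cut at a new therapy.
- **Arm.** Section 12.1 defines the safety population "with treatment assignments designated according to actual study treatment received". Off-study SBRT is not study treatment, so a man randomised to apalutamide alone stays in that column.

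Three other provisions bear on the point. Section 4.4 follows AEs "until 30 days after completion of treatment, removal from study, or until death, whichever occurs first". Section 8.6 adds: "In the event of disease progression per PCWG3 or initiation of a new non-protocol therapy, patients will be discontinued from the study". Section 7.1.7 states: "All concomitant medication and concurrent therapies will be documented from screening until 30 days after the last dose of study drug", with dates captured.

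**The concern.** The safety of apalutamide combined with SBRT is secondary objective 2. Readers will judge what SBRT adds by comparing AE rates between two columns of about 30 men. If off-study SBRT toxicity is counted in the apalutamide-alone column, that column no longer shows apalutamide alone.

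More such events in the apalutamide-alone arm (Arm A) than in the combination arm (Arm B) would shrink the visible difference and make SBRT look slightly safer than it is. Such an imbalance is plausible. Arm A men enter with lesions judged amenable to SBRT that the protocol leaves unirradiated, and the trial's hypothesis is that they do worse. The documents do not state that off-study SBRT will be more frequent in Arm A.

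**Working it through.** **The plan's own figure.** The documents give no rate, effect size or power for the safety comparison. The only power figure is 84% for the primary endpoint (Section 12.2.5). With 30 × 0.9 = 27 evaluable men per arm, 25% versus 2.5%, and a one-sided Fisher's exact test at 0.10, full enumeration gives 83.6%. No AE quantity enters that calculation.

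**Who can be affected.** Apalutamide must stop at or near progression, off-study SBRT must start within 30 days of the last dose, and the AE must begin before that window ends. A man who completes 52 weeks and progresses more than 30 days later is outside it.

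**Inputs**
- From the documents: 30 men per arm; about 12 months of treatment; median time to PSA progression 24.0 months, lower limit 16.3 (Section 1.1.3, non-metastatic CRPC subgroup of the phase 2 study).
- Assumed: exponential times; hazard ratio 0.5 for Arm B; 10% to 50% of progressors start off-study SBRT inside the window; 20% to 40% of those have an acute AE from it.

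**Step 1, progression by month 12**
- Arm A: 1 − 0.5^(12/24) = 29.3%, or 8.8 of 30.
- Arm B: 1 − 0.5^(0.5 × 12/24) = 15.9%, or 4.8 of 30.

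**Step 2, points added = progression × uptake × AE rate**

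| | Low (0.1 × 0.2) | High (0.5 × 0.4) |
|---|---|---|
| Arm A | 0.6 | 5.9 |
| Arm B | 0.3 | 3.2 |
| Net = (29.3% − 15.9%) × product | 0.3 | 2.7 |
| Net in men of 30 | 0.08 | 0.8 |

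With hazard ratio 1.0 and equal uptake, the net is zero.

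**Step 3, sensitivity**
- At the 16.3-month limit, progression is 1 − 0.5^(12/16.3) = 40.0% in Arm A and 1 − 0.5^(6/16.3) = 22.5% in Arm B. The net is 17.5% × 0.02 to 0.20 = 0.35 to 3.5 points, at most about one man.
- A man who already has the event adds nothing. With assumed background rates of 30% (Arm A) and 50% (Arm B) and the 24.0-month median, the high case is 29.3% × 0.2 × 0.7 = 4.1 points against 15.9% × 0.2 × 0.5 = 1.6, a net of 2.5. With equal progression and uptake, the high case leaves 4.1 − 2.9 = 1.2 points, only because more Arm B men already have the event.

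**Step 4, the competing end of follow-up.** Section 4.4 can be read in two ways. On one, AE follow-up runs 30 days past removal from study. On the other, it closes at removal itself. Section 8.6 removes men at progression or at any new non-protocol therapy, local or systemic. The second reading would therefore stop collection before off-study SBRT begins. It would also make the systemic-therapy clause in Section 9.3.2 redundant and contradict the 30-day window in 9.3.2, 12.2.2 and Appendix 1. The text does not settle which reading applies.

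**The case against.** The strongest reply is that little depends on this. Safety is summarised descriptively, with no test or decision rule. Protocol SBRT must start within 90 days of apalutamide, so its acute toxicity is captured well inside the window. Few men will start off-study SBRT within 30 days of the last dose: progression needs a confirmatory PSA, the optional scan has a 28-day window, and radiotherapy planning takes time. Section 12.2.2 also tabulates AEs by relationship, and toxicity from off-study SBRT should not be judged related to study treatment. All of this limits the size, and the low end of the range is the more likely.

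It does not remove the point. Section 9.1.5 attributes events to the study drug only, whereas Appendix 6 section 3.1 also allows attribution to a study procedure. The related-AE table is therefore not a settled way of isolating SBRT toxicity, and the all-cause table still matters. Section 7.1.7 makes affected events identifiable, but no analysis rule uses those dates.

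A reader might infer three stronger things.

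- *The bias can run only one way.* The documents do not support this. Off-study SBRT is allowed in both arms. Earlier systemic therapy in Arm A would also cut off non-serious reporting sooner there, which pushes the other way.
- *The systemic-therapy clause is the only early end to AE follow-up.* Sections 4.4 and 8.6 may supply another.
- *The analysis treats a man as observed to day 30 although collection stopped earlier.* Section 12.2.2 counts events that were reported, over men treated. It computes no person-time, so this mismatch is weak.

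**Conclusion.** The point holds as a minor gap in the safety analysis. As written, Section 12.2.2 allows toxicity from off-study SBRT to be tabulated under a man's study arm, including apalutamide alone. The direction, a slight understatement of the toxicity SBRT adds, is plausible but depends on more such cases in Arm A.

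The net size is about 0.3 to 2.7 points, under one man in 30. It rests on the 24.0-month median from a different population and on assumed exponential times, hazard ratio 0.5, uptake of 10% to 50% and an acute AE rate of 20% to 40%. The documents supply none of these assumed values. If progression and uptake are equal between arms, the simple sum gives zero. The primary endpoint, sample size and power are not affected. Sections 4.4 and 8.6 need to be reconciled with 9.3.2, 12.2.2 and Appendix 1 footnote 2 whatever the size.

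**What to change.** In Section 12.2.2, limit the main by-arm treatment-emergent summary to AEs with onset before the start of any non-protocol anti-cancer therapy, including off-study SBRT or other local treatment, and within 30 days of the last apalutamide dose. Take the start dates from the record required by Section 7.1.7. List AEs and SAEs with later onset separately by arm, flagged with the therapy started.

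Make Sections 4.4, 8.6 and 9.3.2 and Appendix 1 footnote 2 consistent with this rule, and state plainly whether removal from study ends AE collection. Confirm that therapy dates are still recorded to day 30 for men removed at progression, since the rule depends on them.

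Separating events at analysis is better than widening the collection stop to local therapy, which would lose late apalutamide events.

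The cost is one or two sentences in 12.2.2 and aligned wording in four places, with no added visits or data items. The downside is that a few late events move from the main table to a flagged listing.
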